### **Approach**

**The aim of this project is to conduct a pilot study to investigate the feasibility and initial efficacy of applying FE to individuals with MS to improve motor function, cognitive function, and QOL.**

**Experimental Overview:** A pilot study is proposed in which 20 individuals with MS presenting with an Expanded Disability Status Scale score between 2.0 and 6.5 will be eligible to participate. Participants will be screened using the American College of Sports Medicine Exercise Preparticipation Health Screening algorithm. The potential participant's physician will be notified of the study protocol and their patient's desire to participate. Eligible participants will undergo clinical and biomechanical assessments evaluating lower extremity function, processing speed, memory, and self-reported quality of life at baseline and post-intervention. Following baseline testing, participants will be randomized to undergo FE (n=10) or VE (n=10). Randomization will be stratified based on EDSS level (2.0-4.0 vs. 4.5-6.5) to facilitate comparable levels of disability in both groups. Participants in both groups will attend exercise sessions twice a week for 12 weeks. The FE intervention will consist of forced-rate aerobic exercise on a stationary semi-recumbent bicycle. Target cadence will be 80 revolutions per minute (RPM). Should the participant not tolerate the 80 RPM cadence, a self-selected cadence will be used initially, and increased by 5 RPM each session until the target cadence of 80 RPM is achieved. The VE intervention will be identical to FE, except participants will cycle at a self-selected cadence on a semi-recumbent stationary cycle ergometer without assistance from the motor. Aerobic intensity for both groups will be monitored continuously throughout the exercise using a heart rate chest strap. Target heart rate will be prescribed at 60-80% of the individual's age-predicted maximum. Following a 5-minute

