warm-up, participants will complete a 35-minute main exercise set with the goal of maintaining their heart rate within the prescribed target zone. A 5-minute cool-down will occur immediately at the end of the 35-minute main exercise set. For the FE group, the cadence during warm up and cool down will be 15-20% less than the target cadence for the main exercise set (80 RPM) during the main exercise set. Water will be provided to the participant ad libitum, but all will be encouraged to drink 16-24 ounces during the exercise session. Cooling vests will be available to participants to avoid overheating as indicated. Rest breaks will be provided as requested, but all participants will be encouraged to progress to an entire 45-minute session without rest breaks.

**Recruitment and Sample:** Physicians and advance practice clinicians within the Mellen Center who would otherwise prescribe physical therapy to their patients will provide prospective participants with a study brochure. Should they express interest in learning more about the study, the study coordinator will call them to follow up. The study team may use MyChart as a way to contact eligible patients with an IRB approved flyer and/or brochure. Twenty-four patients will be recruited for this pilot feasibility study.

**Aim 1: To determine the feasibility of applying FE or VE training to individuals with MS.** Primary outcomes to determine feasibility will include measures of exercise compliance (percent of sessions attended, time spent exercising, time spent within target heart rate zone) and the absence of adverse events. The secondary outcomes will include change in levels fatigue and physical activity.

**Hypothesis 1:** Participants will comply with the FE or VE intervention (exercise frequency, time, and intensity) at  $\geq 90\%$  of the prescribed values and will present with no worsening fatigue or levels of sedentary activity following the FE or VE intervention.

**Aim 2: To determine the effects of a 12-week FE or VE intervention on motor function.** The primary outcome is change in biomechanical characteristics of gait. Secondary outcomes include changes in walking capacity, balance, manual dexterity test (MDT), and timed up and go (iTUG).

**Hypothesis 2:** Improvements in gait biomechanics and walking capacity will be observed following the 12-week FE intervention.

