### **Outcomes:**

**Analysis of Feasibility (Aim 1):** Measures of compliance will determine feasibility of individuals with MS to complete the FE intervention. Self-reported fatigue will be measured using the Modified Fatigue Impact Scale. Activity levels will be measured using a Garmin Vivofit 4 body-worn activity monitor. The absence of adverse events will demonstrate safety of FE in MS.

**Biomechanical Gait Assessment (Aim 2):** The CAREN system is a complete biomechanical assessment system with 10 Vicon cameras, split-belt treadmill with two force plates, and D-flow software. Twenty-five retro-reflective markers will be placed at anatomic landmarks identified for LE assessment. Participants will walk at a self-selected pace for two 2-minute trials. The following biomechanical outcomes will be calculated: 1) spatio-temporal: velocity; cadence, step length, percentage of gait cycle spent in swing and stance phase, single and double limb support time and percentage; 2) Kinematic: hip and knee flexion and extension; ankle dorsi- and plantar-flexion; pelvic obliquity, rotation and tilt. To determine changes in overground walking, gait analysis will also be conducted using the Zeno Instrumented walkway. Participants will walk at a self-selected pace and fast pace for four lengths for each condition along the 15' Zeno Instrumented walkway. The following spatio-temporal outcomes will be calculated: velocity; cadence, step length, percentage of gait cycle spent in swing and stance phase, single and double limb support time and percentage. Lastly, the Timed up and Go will be administered.

**Non-Motor Function Data (Aim 3):** The PROMIS-29 will be administered to determine self-reported quality of life. The multiple sclerosis performance test (MSPT) and two measures of episodic memory, the California Verbal Learning Test and the Brief Visuospatial Memory Test, will be administered to examine change in cognitive function. All will be administered to determine feasibility with respect to administration approach, sensitivity to detect change over time, and time requirements for a future clinical trial.

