The Therapeutic Effects of Forced Aerobic Exercise in Multiple Sclerosis

Statistical Analysis

NCT Number: 04906057

Document Date: 07/15/2021

Section of Biostatistics
Quantitative Health Sciences/ JJN-3
[name]

IRB 19-1003: Feasibility study investigating forced and voluntary rate aerobic cycling in persons with multiple sclerosis

Statistical Methods:

Demographics, patient characteristics and exercise parameters will be summarized by mean with standard deviation or median with interquartile range for continuous variables, and count with percentage for categorical variables. Patients will be stratified by exercise groups (FE vs VE).

Changes in motor and non-motor functions from baseline to end of treatment will be examined by paired sample t-tests.

Changes in Klotho level from pre- to post-exercise will be examined by paired sample t-tests, at both first exercise session and last exercise session. Changes in Klotho level from first exercise session to last exercise session will also be examined by paired sample t-tests, at both pre-exercise and post-exercise. Mixed-effect model will be used to examine if there is significant acute change (from pre- to post-exercise) or long-term change (from first to last exercise session) in Klotho level. Patient random effect and exercise group indicator (FE vs VE) will be included in the model. Changes in Neurofilament light (NFL) from baseline to end of treatment will be examined by paired sample t-test.

Effects of exercise parameters on walking outcomes at end of treatment will be examined by linear regressions. Exercise parameters will be in separate models and baseline values of walking outcomes will be adjusted for in the models.

Outcomes measured at end of treatment will be compared between groups using linear regressions. Baseline values of outcomes will be adjusted for in the models.

Changes in exercise parameters over sessions will be examined by mixed-effect models, where session is the independent variable. Patient random effect will be included in the model. Group difference in changes in exercise cadence over sessions will be examined by mixed-effect models, where independent variables include session, group and interaction between session and group. Patient random effect will be included in the model.

We will also compare variables (motor and non-motor functions) between baseline1 and baseline2 using paired sample t-tests.

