P<0.05 will be considered as statistically significant.

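### For the Aim 3 measures, the SAP's paired t-tests test mean shift but report neither measurement error nor responsiveness, which the protocol's sensitivity-to-change goal needs

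*SAP*

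**What the plan says.** Protocol, Outcomes, Non-Motor Function Data (Aim 3). This paragraph names PROMIS-29 ("The PROMIS-29 will be administered to determine self-reported quality of life"), MSPT, CVLT and BVMT. It then says that all of them are given to judge feasibility in three respects: how they are administered, and their "sensitivity to detect change over time, and time requirements for a future clinical trial". No such goal is stated for the gait, walkway or Timed Up and Go measures.

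SAP, Statistical Methods. The only planned use of the repeat baseline is to compare motor and non-motor variables "between baseline1 and baseline2 using paired sample t-tests". No purpose is given for the comparison. Change in motor and non-motor function from baseline to end of treatment is also examined by paired t-tests. The decision rule is "P<0.05 will be considered as statistically significant". The SAP names no intraclass correlation (ICC), standard error of measurement (SEM), minimal detectable change (MDC), limits of agreement or standardised response mean, and no confidence interval for either comparison.

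Protocol, Approach. The Experimental Overview describes assessment at baseline and after the intervention. It mentions no second baseline and no interval between two baselines. The sample size appears as "A pilot study is proposed in which 20 individuals with MS" and, under Recruitment and Sample, as "Twenty-four patients will be recruited for this pilot feasibility study".

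**The concern.** Learning whether a measure is sensitive to change takes two quantities: how much scores move when nothing has been done, and how large the change over treatment is compared with its spread. The plan collects data bearing on both but attaches only a significance test to each. A p-value mixes the size of the mean shift, the noise and the sample size into one number, so neither quantity can be read from it.

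Two things are at stake. First, the pilot could finish without reporting what its Aim 3 paragraph set out to learn about these four instruments. Second, a baseline comparison with p>0.05 could be taken as showing that a measure is stable, when the test has little power at this sample size and a noisy measure passes it more easily than a precise one.

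**Working it through.** The documents give no SD, retest correlation, effect size or power calculation, so there is no planned figure to reproduce. The figures below are illustrations.

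**Inputs.** n=20 (Experimental Overview) and n=24 (Recruitment and Sample). Alpha is 0.05 (SAP), assumed two-sided because the SAP does not say. The retest correlation r is an assumption, shown over a range. Scores are scaled so that the SD of a single assessment is 1. With equal variances at the two baselines:

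- SD of differences = √(2(1−r))
- SEM = √(1−r)
- MDC95 = 1.96 × √2 × SEM = 1.96 × √(2(1−r))

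**1. What a non-significant baseline comparison excludes.** From the noncentral t distribution, a paired t-test has 80% power for a mean shift of 0.660 SD of the differences at n=20 and 0.597 at n=24. Multiplying by √(2(1−r)) converts this to SDs of a single assessment:

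| r (assumed) | SD of differences | Shift, n=20 | Shift, n=24 | MDC95 |
|---|---|---|---|---|
| 0.6 | 0.894 | 0.59 | 0.53 | 1.75 |
| 0.8 | 0.632 | 0.42 | 0.38 | 1.24 |
| 0.9 | 0.447 | 0.30 | 0.27 | 0.88 |

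Even an observed mean difference of exactly zero at n=20 would have a 95% CI of ±2.093/√20 = ±0.47 SD of the differences.

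**2. Whether the test responds to repeatability.** With no true shift, simulation (20,000 runs per setting) gave rejection rates of 4.6% to 5.2% for r from 0.3 to 0.95. Over that range MDC95 runs from 2.32 to 0.62 SD, almost a fourfold difference that the test does not register. With the same true shift of 0.3 SD (assumed):

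| r (assumed) | Rejects, n=20 | Rejects, n=24 |
|---|---|---|
| 0.3 | 19% | 22% |
| 0.5 | 25% | 29% |
| 0.7 | 38% | 44% |
| 0.9 | 81% | 88% |
| 0.95 | 98% | 99% |

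The more repeatable measure is the one more likely to be flagged, so read as a stability check the test ranks measures the wrong way round.

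**3. What the same data could give, and how precisely.** The SD of differences is computed inside the paired t-test. SEM is that SD divided by √2, and MDC95 is 1.96 times it. For baseline-to-end change, the standardised response mean is mean change divided by SD of change, which equals t/√n. Expected precision:

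- ICC observed at 0.8, n=20, one-way F method: F = (1+0.8)/(1−0.8) = 9. The lower limit uses 9/2.482 = 3.63, giving (3.63−1)/(3.63+1) = 0.57. The upper limit uses 9 × 2.509 = 22.6, giving 21.6/23.6 = 0.92.
- SD of differences, and hence SEM and MDC: the 95% CI runs from 0.76 to 1.46 times the estimate at n=20, and from 0.78 to 1.40 times at n=24.

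**The case against.** The strongest reply is that the baseline1–baseline2 test is being faulted for a job nobody gave it. The SAP states no purpose for it, the Aim 3 paragraph does not mention two baselines, and a paired t-test is an ordinary check for practice effect or drift. This stands. A reader might infer that the two baselines were set up to deliver the sensitivity goal, or that the t-test is the wrong test and should go. The documents support neither.

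A reader might also extend the goal to every measure in the SAP comparison. The protocol states it only for PROMIS-29, MSPT, CVLT and BVMT, so for the motor measures the addition is optional.

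Nor is repeatability the same as sensitivity to change, which also depends on the change over treatment. The SAP does analyse that change, but only by paired t-test, so responsiveness goes unquantified there too. An ICC and MDC alone would not meet the goal either.

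It would be too strong to say that measurement error is lost or that a future trial cannot be planned. The SD of differences can be recovered from the same data. A parallel-group trial is usually sized from the outcome SD and the baseline-to-follow-up correlation, and the 12-week data supply both. The gap is in what the SAP commits to report.

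Finally, baseline2 is undefined. If the interval is long, or something is done to participants within it, ICC and MDC would mix true change with error. This also stands, and it is why the timing has to be stated.

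**Conclusion.** The point holds in limited form. For the four Aim 3 measures, the protocol states a sensitivity-to-change goal, and the SAP's two within-person analyses test mean shift without quantifying measurement error or responsiveness. A non-significant baseline comparison would be weak evidence of stability: 80% power is reached only at about 0.66 SD of the differences with 20 participants and about 0.60 with 24, so the conflict between the two sample sizes does not alter the conclusion. Those two figures rest on a two-sided 5% test. The figures in SDs of a single assessment also rest on the assumed retest correlations and the 0.3 SD shift. This is an inexpensive improvement to a pilot's reporting. It does not make the planned tests invalid.

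**What to change.** In the SAP, Statistical Methods:

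1. Keep the baseline1–baseline2 paired t-test, describe it as a check for practice effect or drift, and report the mean difference with its 95% CI. State that p>0.05 will not be taken as evidence of stability.
2. For PROMIS-29, MSPT, CVLT and BVMT, and optionally the motor measures, report the ICC (naming its form), SEM and MDC from the two baselines, each with a 95% CI.
3. For the same measures, report a standardised response mean for baseline-to-end change.
4. In both documents, define baseline2: when it occurs, and whether anything is done to participants between the two baselines. Interpret ICC, SEM and MDC as measurement error only if the interval is a true retest without intervention.

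The cost is a few lines of analysis on data the SAP already uses, plus a sentence or two on timing. The intervals will be wide, as the ICC example shows, and should be presented as planning ranges.
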